The focus of Aim 2 is to compare medical care utilization, patient burden, and impact on patient time and activities for individuals participating in OSMT with those receiving UC. Assessment of these measures is critical for patient-centered care, in order to minimize the financial burdens and non-financial impacts (e.g., time commitment) of new interventions. To address hypotheses 2.1 and 2.2, we will collect detailed information on use of medical care services and supplies related to ostomy care, patient burden for these services and supplies, required patient and caregiver time for ostomy care, interference with employment and volunteer activities, and perceived financial burden. Details regarding the four types of information to be collected for Aim 2 are presented below. We also provide information on assessment on study activities to address replication of the OSMT intervention (Question 2.2).

12.4 Ostomy-Related Medical Care Supplies and Services. We will collect information from study participants on their use of supplies and services related to ostomy care and their out-of-pocket expenses for these supplies/services. Ostomy-related services/supplies will be categorized in two separate groups:

- Medical care encounters and ostomy supplies including: OCN visits; other ostomy-related medical care encounters (including physician and ED visits); surgical revision of stoma; ostomy appliances, wafers, bags; bowel medications; and skin medications.
- Other equipment, household modifications related to ostomy and ostomy care, including: waterproof covers on for mattresses and furniture; bathroom remodels to accommodate ostomy care; special clothing to cover ostomy bag; alteration of clothing to cover ostomy bag, and transportation to and parking for ostomy-related medical care.

12.5 Ostomy-Related Time Requirements. We will also collect ostomy-related time requirements, that is, patient time required to obtain ostomy care, perform ostomy bag and wafer management, and clean ostomy bag spills. We will also ask study participants about use of both formal and informal CGs, time for caregiving activities related to ostomy care, and types of assistance (e.g., with housekeeping and shopping) required due to ostomy and ostomy care.

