15.7 Appendix 7a Burden of Ostomy Care Survey (full survey, baseline and followup)

BURDEN OF OSTOMY CARE

This study aims to collect data on the burden associated with families' use of ostomy care and supplies, including ostomy-related medications, ostomy-related health care visits, travel costs to obtain ostomy-related care and supplies, and time spent on ostomy management tasks. We ask that you please answer these questions while thinking specifically about the burden of ostomy-related care. This is not a test; please give us your best estimates based on your personal experience.

1. What kind of Ostomy do you have? Colostomy Ileostomy Urostomy Other

2. In-person Visits with Wound and Ostomy Care Nurse in the past 4 weeks:

- a. Did you visit a Nurse in person in the past 4 weeks (at a medical office, hospital, and/or in your home)? No (If NO, skip to Question 3. below.) Yes
- b. **If YES:** How many times did you visit the Nurse in the past 4 weeks? 1 2 3-4 5-8 More than 8

Please answer questions 2c through 2g thinking specifically about your most recent visit to the Nurse.

- c. How much do you typically pay out-of-pocket for each Nurse visit (copayments, deductibles, or other costs for the visit that weren't covered by your insurance)?
 Nothing \$1-\$10 \$11-\$25 \$26-\$50 \$51-\$75 \$76-\$100 \$101+
- d. Did you have to travel to see the Nurse for your most recent visit? No (If NO, skip to Question 3. below.) Yes
- e. How much do you typically pay out-of-pocket to get to and from each Nurse visit (such as the cost for taxi, bus, or parking)? \$1-\$5 \$6-10 \$11-15 \$16-\$25 \$26-\$50 \$51-\$100 \$101+
- f. Approximately how far did you have to travel to the Nurse Visit location? 1-4 miles 5-8 mi. More than 8 mi.
- g. Approximately how much time did it take you to get from your home to the Nurse Visit location? 1-10 mins 11-30 mins More than 30 mins

3. Telephone and/or email consultations with a Wound and Ostomy Care Nurse in the past 4 weeks:

- a. Did you have any telephone and/or web consultations with the Nurse in the past 4 weeks? No (If NO, skip to Question 4 below.) Yes
- b. **If YES:** How many telephone and/or web consultations have you had with a Wound and Ostomy Care Nurse over the past 4 weeks? 1 2 3-4 5-8 More than 8

Please answer Question 3c thinking specifically about your most recent telephone or web consultation with the Nurse.

- c. How much did you have to pay out-of-pocket for this Nurse consultation?

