 Nothing \$1-\$10 \$11-\$25 \$26-\$50 \$51-\$75 \$76-\$100 \$101+

4. In-person Visits with a Physician for stoma and/or bowel function problems in the past 4 weeks:

- a. Did you visit a Physician in person for stoma and/or bowel function problems in the past 4 weeks? No (If NO, skip to Question 5. below.) Yes
- b. **If YES:** How many times did you visit the Physician in the past 4 weeks?
 1 2 3-4 5-8 More than 8

Please answer Questions 4c through 4g thinking specifically about your most recent visit to the Physician.

- c. How much do you typically pay out-of-pocket for each Physician visit (copayments, deductibles, or other costs for the visit that weren't covered by your insurance)?
 Nothing \$1-\$10 \$11-\$25 \$26-\$50 \$51-\$75 \$76-\$100 \$101+
 - d. Did you have to travel to see the Physician for your most recent visit? No (If NO, skip to Question 5. below.) Yes
 - e. How much do you typically pay out-of-pocket to get to and from each Physician visit (such as the cost for taxi, bus, or parking)? \$1-\$5 \$6-10 \$11-15 \$16-\$25 \$26-\$50 \$51-\$100 \$101+
 - f. Approximately how far did you have to travel to the Physician visit location? 1-4 miles 5-8 mi. More than 8 mi.
 - g. Approximately how much time did it take you to get from your home to the Physician visit location? 1-10 mins 11-30 mins More than 30 mins
5. **What other sources do you use to find more information about your ostomy and daily care?** (Fill in all that apply)
 Internet Magazines Other people with an ostomy Support Group
 Other (please specify)
-
6. **If you wear a pouch and have encountered any problems with it, please explain below what those problems are/were?**
-
-
-
7. **How long was it before you felt comfortable with your daily ostomy care?**
 0 < 1 month 1-12 months 12+ months I am still not comfortable
8. **On average, how long does it take to do your daily ostomy care?**
 0-5 min 5-10 min 10-15 min 15-30 min 30-60min More than 60min
9. **Do you irrigate (flush) your ostomy?**
 Yes → Please answer 9a. I used to but stopped → Please answer 9b No Please skip to 10.
- 9a. **IF YES, How often do you irrigate your ostomy?** Once a day Every other day Every third day Other (please specify) _____
- 9b. **If you used to irrigate but stopped, why did you stop?** Pain Hernia Too time consuming
 Other (Please specify) _____
10. **Please describe the reasons you irrigate your ostomy.** (Check all that apply)

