 To control timing of bowel movements To avoid blockage To avoid pain Convenience
 Other (please specify)
11. **Telephone and/or email consultations with a Physician for stoma and/or bowel function problems in the past 4 weeks:**
- a. Did you have any telephone and/or web consultations with a Physician for stoma and/or bowel function problems in the past 4 weeks? No (**IF NO**, skip to Question 12. below.) Yes
 - b. **IF YES:** How many telephone and/or web consultations have you had with a Physician over the past 4 weeks? 1 2 3-4 5-8 More than 8

Please answer Question 11c thinking specifically about your most recent telephone or web consultation with the Physician.

- c. How much did you have to pay out-of-pocket for this consultation?
 Nothing \$1-\$10 \$11-\$25 \$26-\$50 \$51-\$75 \$76-\$100 \$101+

12. Emergency Room visits for stoma and/or bowel function problems in the past 4 weeks:

- a. Did you have any visits to the Emergency Room for stoma and/or bowel function problems in the past 4 weeks? No (IF NO, skip to Question 13. below.) Yes
 b. **IF YES:** How many times did you visit the Emergency Room for stoma and/or bowel function problems in the past 4 weeks? 1 2 3-4 5-8 More than 8

Please answer Question 12c thinking specifically about your most Emergency Room visit for stoma and/or bowel function problems.

- c. How much did you pay out-of-pocket for your most recent ER visit (copayments, deductibles, or other costs for the visit that weren't covered by your insurance)?
 \$0 \$1-\$5 \$6-10 \$11-15 \$16-\$25 \$26-\$50 \$51-\$100 \$101+
 d. How much did you pay out-of-pocket to get to and from this ER visit (such as the cost for taxi, bus, or parking)? \$0 \$1-\$5 \$6-10 \$11-15 \$16-\$25 \$26-\$50 \$51-\$100 \$101+
 e. Approximately how far did you have to travel to the ER visit location? 1-4 miles 5-8 mi. More than 8 mi.
 f. Approximately how much time did it take you to get from your home to the ER visit location? 1-4 minutes 5-8 min. More than 8 min.

13. Urgent Care visits for stoma and/or bowel function problems in the past 4 weeks:

- a. Did you have any visits to an Urgent Care facility for stoma and/or bowel function problems in the past 4 weeks? No (IF NO, skip to Question 14 below.) Yes
 b. **IF YES:** How many times did you visit an Urgent Care center for stoma and/or bowel function problems in the past 4 weeks? 1 2 3-4 5-8 More than 8

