 - i. Medication _____ Number of days used (0 to 7) _____
 - ii. Medication _____ Number of days used (0 to 7) _____
 - iii. Medication _____ Number of days used (0 to 7) _____

19. How much have you spent on purchases of ostomy appliances (including wafers and bags in total over the past 4 weeks)? \$0 \$1-\$25 \$26-50 \$51-100 \$100-\$150 \$150-\$200 \$200-\$250 over \$250

20. About how many times a day do you empty your drainable ostomy bag (or discard your closed/disposable bag)?

- None 1-4 5-8 More than 8

21. Over the past 4 weeks, what was the highest number of bag emptyings in a 24-hour period?

- None 1-4 5-8 More than 8

22. Over the past 4 weeks, what was the lowest number of bag emptyings in a 24-hour period?

- None 1-4 5-8 More than 8

23. How often do you typically discard a used bag and use a new bag?

- At every emptying Once a day Once every 2-3 days Less often

24. How much time does it usually take you to empty/dispose your bag?

- 1-5 minutes 5-10 minutes 10-15 minutes More than 15 minutes

25. How often do you typically change your wafer on a typical week? 1 2 3 4-7 More than 7

26. How much time does it usually take you to change your wafer and bag?

- 1-15 minutes 16-30 minutes 30-45 minutes 45-60 minutes More than 60 minutes

27. Do you usually receive help caring for your stoma and changing your ostomy appliance?

- a. No (skip to Question 27 below)
- b. Yes IF Yes, please check who your helper(s) is(are):
 Spouse/Significant Other Other family member Friend Home care nurse Other Paid Caregiver Other (please specify) _____

28. Has your bag leaked at any time over the past 4 weeks?

- a. No (skip to Question 28 below)
- b. Yes **IF YES**, how many times? 1-4 5-8 More than 8
- c. How many of these times involved a full spillage of your bag contents? 1-4 5-8
More than 8
- d. How much time does it require to clean up after a bag leak or spill? 1-30 minutes 31-60 mins.
More than 60 mins

29. Do you have waterproof covers on your mattress and primary chair(s)?

- a. No → Skip to Question 29 below.
- b. Yes **IF YES**, how much did you spend to purchase them?
\$0 \$1-\$10 \$11-\$25 \$26-\$50 \$51-\$75 \$76-\$100 \$101-\$150 \$151+

30. Do you have to make alterations to your clothing to accommodate your ostomy appliance?

- a. No **IF NO**, skip to Question 30 below.
- b. Yes **IF YES**, do you make these modifications yourself?
 - i. No
 - ii. Yes → **IF YES**, How much do you spend for these modifications?

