\$0 \$1-\$5 \$6-\$10 \$11-\$15 \$16-\$25 \$26-\$50 \$51-\$100 \$101+

31. Do you make some or all your own clothes because you have an ostomy and nothing in the clothing stores will fit you appropriately?

- a. No → **IF NO**, skip to Question 32 below.
- b. Yes → **IF YES**, how much do you spend to make your own clothes in a year?
\$0 \$1-\$5 \$6-\$10 \$11-\$15 \$16-\$25 \$26-\$50 \$51-\$100 \$101+

32. Did you purchase any fashion accessories specifically made for someone with an Ostomy (for example, fashion wraps, special underwear, Stealth belt)?

- a. No → **IF NO**, skip to Question 33 below.
- b. Yes → **IF YES**, how much did you spend to purchase your special underwear/girdle/body wrap?
\$0 \$1-\$5 \$6-\$10 \$11-\$15 \$16-\$25 \$26-\$50 \$51-\$100 \$101+

33. Do you wear a hernia belt?

- a. No → **IF NO**, skip to Question 34 below.
- b. Yes → **IF YES**, how much did you spend to purchase your hernia belt(s)?
\$0 \$1-\$5 \$6-\$10 \$11-\$15 \$16-\$25 \$26-\$50 \$51-\$100 \$101+

34. How would you describe your current employment?

(Please select only one)

- Full time
- Part time
- Retired and not working another job
- Home maker
- Temporarily laid off
- Unemployed and looking for work
- Unemployed and **not** looking for work
- On disability

Other: (please explain) _____

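### Several Aim 2 burden items cannot record a true zero (full spills, nurse and physician travel cost) and four spending items have no recall period, so these quantities are mismeasured in a direction the documents cannot settle

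*Protocol*

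**What the plan says.** **Full spills.** Protocol Appendix 7a item 28 asks whether the bag leaked in the past 4 weeks, then how many times (28b), then "How many of these times involved a full spillage of your bag contents" (28c), then how long clean-up takes (28d). The options in 28c are 1-4, 5-8 and more than 8. Appendix 7b item 12.i repeats the question with the same three options. Items 20 to 22 of 7a use the same bands preceded by None.

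**Travel cost.** Item 2d asks "Did you have to travel to see the Nurse for your most recent visit" and sends non-travellers past the rest of the block. Item 2e then asks "How much do you typically pay out-of-pocket to get to and from each Nurse visit", with a lowest band of 1 to 5 dollars. Items 4d and 4e do the same for physicians: "How much do you typically pay out-of-pocket to get to and from each Physician visit". The parallel emergency item 12d, "How much did you pay out-of-pocket to get to and from this ER visit", offers 0 dollars, as does urgent-care item 13d.

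**Spending.** Item 29b asks, about waterproof covers, "how much did you spend to purchase them". Items 30b.ii (clothing alterations), 32b (accessories) and 33b (hernia belt) likewise name no period. Item 19 (appliances) covers the past 4 weeks and item 31b (making clothes) covers a year.

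**Use.** Section 12.4 counts covers, clothing and "transportation to and parking for ostomy-related medical care" among the Aim 2 resources, and section 12.5 counts time spent cleaning up spills. Hypothesis 2.1 (section 2.2) compares family resources over the 6 months after the programme. Section 8.2 gives 7a at baseline and at 6-month follow-up, and 7b at the end of the sessions.

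**The concern.** A count that can be zero needs a zero on the form. Without one, a respondent who follows the form must choose between a false positive answer and a blank, and the information cannot be recovered after collection. Fewer full spills is a plausible benefit of training in pouch care. Yet a move from some full spills to none cannot be recorded in 28c while any leak continues.

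The undated items raise a different problem. Section 5.1 sets no maximum time since surgery. A belt or mattress cover bought well before randomisation can therefore be reported at follow-up as though it belonged to the period that Hypothesis 2.1 addresses.

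Aim 2 is the trial's stated secondary objective. Neither the protocol nor the SAP says how these items are scored, how a blank is handled, or whether the baseline answer is subtracted.

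**Working it through.** The documents give no rate, SD or power for any Aim 2 item, so there is no stated figure to reproduce. The check is of the form's own options, followed by illustrations in which **every rate is an assumption**. Power is for two proportions, two-sided 5%, with the 75 completers per arm targeted in section 12.13.

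**1. Form against form**

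| Item | Zero offered? | Period stated? | Sibling item |
|---|---|---|---|
| 7a 28c, 7b 12.i | No | Past 4 weeks, from the stem | 20-22: same bands with None |
| 7a 2e, 4e | No | Per typical visit | 12d, 13d: 0 dollars offered |
| 7a 29b, 30b.ii, 32b, 33b | Yes | No | 19: 4 weeks; 31b: one year |

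The missing spill option appears on both forms and the sibling items show theirs, so loss in text extraction is unlikely.

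**2. Any full spill, if every true zero is marked 1-4**

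True proportion = leak rate × share of leakers with a full spill. Recorded proportion = leak rate.

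| Leak rate, usual care vs programme | Spill share among leakers | True difference (power) | Recorded difference (power) |
|---|---|---|---|
| 50% vs 50% | 50% vs 25% | 25.0 − 12.5 = 12.5 points (50%) | 50 − 50 = 0 points |
| 50% vs 40% | 50% vs 25% | 25.0 − 10.0 = 15 points (68%) | 50 − 40 = 10 points (23%) |
| 50% vs 35% | 30% vs 30% | 15.0 − 10.5 = 4.5 points (13%) | 50 − 35 = 15 points (46%) |

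The first two rows dilute the difference and the third inflates it. If only half the true zeros are marked 1-4 and the rest count as no spill, the recorded differences are about 6, 12.5 and 10 points. The direction in each row is unchanged.

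**3. Travel cost**

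Mean overstatement per visit involving travel = share truly free × amount assigned, where the amount lies between 1 and 5 dollars.

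- Low end: 0.20 × 1 = 0.20 dollars.
- High end: 0.80 × 5 = 4.00 dollars.
- No single visit can be overstated by more than 5 dollars.

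**4. Undated purchases, as any purchase yes or no**

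Recorded proportion = e + (1 − e) × p, where e is the share who bought earlier (equal in both arms) and p is the true 6-month rate, taken as 30% vs 15%.

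| e | Recorded | Difference | Power |
|---|---|---|---|
| 0% | 30% vs 15% | 15 points | 60% |
| 20% | 44% vs 32% | 12 points | 33% |
| 40% | 58% vs 49% | 9 points | 20% |
| 60% | 72% vs 66% | 6 points | 12% |

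**5. Undated purchases, as mean spending**

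Randomisation balances old spending in expectation, so the absolute difference survives apart from noise and open top bands. The relative difference becomes true relative difference × share of spending inside the window. A true 30% cut shows as 0.30 × 0.10 = 3% if a tenth of reported spending is recent, and 0.30 × 0.30 = 9% if three tenths is.

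**6. What the procedures recover**

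Section 8.2.9 has staff read marginal notes first, so a zero written on a paper form can be kept. Call-back then requires a missing page or more than 20% of questions missing, so one blank does not trigger it. Section 8.2.6 mentions telephone contact for incomplete surveys more generally, but 8.2.9 sets the criteria. Web entry is the preferred mode under 8.2.4, and the documents do not say whether a respondent can add a note there.

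**The case against.** The strongest reply is that little of Aim 2 depends on these items. Leak occurrence, leak count and clean-up time are asked separately in item 28, and the spill quantity named in section 12.5 is time, which 28d supplies. The full-spill count is not a listed endpoint in section 11.0. The main recurring purchase, item 19, has both a period and a zero. Item 30b.ii is in the present tense, so it does not plainly invite old purchases. Because 7a is also given at baseline, a coarse change score is possible. All of this stands, and it limits the damage to spill severity among people with leaks, small travel sums, and four minor spending items. The change score is weak, though: the answers are banded, the top bands are open (101 or 151 dollars and above), and respondents may have different periods in mind.

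A reader might go further and infer that burden is overstated and arm differences are diluted. The documents do not support that. Nothing makes 28c compulsory, so a true zero may be left blank instead of marked 1-4. Every recorded answer is at least one, but that is not a 100% spill rate in each arm, because the status behind the blanks is unknown. The third row of the spill table shows inflation. Dilution is the expected direction for undated purchases compared at follow-up only, and for spill severity among leakers, but not in general.

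**Conclusion.** The concern holds as a measurement fault. Four questions (28c, 12.i, 2e, 4e) leave a legitimate zero without a valid answer, and four others (29b, 30b.ii, 32b, 33b) do not match the period in Hypothesis 2.1. The form's own sibling items show that zeros and periods were available.

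The travel error is bounded at 5 dollars per visit, and only for people who had a visit and travelled free. For the other items, the size and direction of the effect on the arm comparison depend on leak rates, spill shares, earlier purchasing and answering behaviour, none of which the documents give. The differences and power figures above show what could happen under the stated assumptions; they are not estimates for this trial. Since no scoring rule is specified, bias in a particular planned estimate cannot be demonstrated. Aim 1 is unaffected. The correction is worth making because it is small and right whichever way the error runs.

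**What to change.** - Add None to 7a item 28c and 7b item 12.i, and a 0-dollar option to 7a items 2e and 4e.
- Keep the stems of items 29, 30, 32 and 33, which ask about having, altering, purchasing or wearing something and do not all take a time prefix. On the follow-up form, add a dated sub-question to each, such as: in the past 6 months, how much did you spend on these, with 0 dollars offered. Section 8.1 requests follow-up surveys 6 months after the interim surveys are completed, so that window fits.
- State in the SAP how bands are scored, how blanks are handled, and whether baseline enters the comparison.
- For forms already returned, apply marginal notes first, then treat a blank in 28c, 12.i, 2e or 4e after a positive stem as missing and not as the lowest band. Report such blanks by arm, because they may well be true zeros. Treat the lowest band as possibly including zero, and do not report undated items as 6-month costs.

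**Cost.** A short amendment to the paper and web forms. If enrolment has begun, two form versions must be tracked. The dated sub-question has no baseline counterpart, so it supports a comparison at follow-up and not a change score. Keeping the undated items unchanged leaves a baseline covariate.

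### Three Appendix 7a sub-items (30, 12f, 13f) collect incomplete alteration-cost and travel-time data for the family-cost and patient-time parts of Aim 2

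*Protocol*

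**What the plan says.** Protocol section 12.4 says participants will report their use of ostomy supplies and services and "their out-of-pocket expenses for these supplies/services". Its second category of items ends with "alteration of clothing to cover ostomy bag, and transportation to and parking for ostomy-related medical care". Section 12.5 adds "patient time required to obtain ostomy care". Section 12.7 names a self-administered patient questionnaire as the source for Aim 2. Section 8.2 schedules the full Burden of Ostomy Care survey (Appendix 7a) at baseline and six months, and a short form (Appendix 7b) at the end of the sessions.

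In Appendix 7a, item 30 first asks whether clothing has to be altered for the appliance. Those who say Yes are asked "do you make these modifications yourself". The No branch ends there. The Yes branch continues with "How much do you spend for these modifications".

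Items 12f (emergency room) and 13f (urgent care) ask travel time from home in the bands "1-4 minutes 5-8 min. More than 8 min". Items 2g (ostomy nurse) and 4g (physician) ask the same thing in the bands "1-10 mins 11-30 mins More than 30 mins".

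**The concern.** Section 12.4 does not limit clothing alteration to work done by the participant, but the form records its cost only in that case. Money paid to someone else for alterations is therefore missing by design. If the blank were later treated as zero, family cost would be understated.

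The minute bands in 12f and 13f repeat the numbers of the mile bands directly above them (12e, 13e), which looks like a copying slip. They cannot be placed on the scale used for nurse and physician visits, and the top code has no upper limit. Travel time to emergency and urgent care therefore cannot be described alongside travel time to the other visit types.

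At stake are parts of Hypothesis 2.1 (family resources) and Question 2.1 (family financial burden), together with the patient-time data promised in section 12.5.

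**Working it through.** The plan gives no figure to reproduce here. The check follows the skip path, compares the bands, and adds one illustrative calculation.

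**Item 30, path by path**

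- No alterations needed: the respondent leaves the item.
- Alterations needed, not self-made: nothing further is asked.
- Alterations needed, self-made: spending is asked in dollar bands.

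Spending is recorded on one of the two paths where it can arise. The condition is written into the words of the form, so it does not depend on page layout lost in text extraction. The neighbouring items do not fill the gap: 31 covers making one's own clothes, 32 covers accessories made for ostomy wearers, and 33 covers a hernia belt. Appendix 7b has no clothing item.

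**Travel bands side by side**

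| Visit type | Distance item and bands (miles) | Time item and bands (minutes) |
|---|---|---|
| Nurse | 2f: 1-4, 5-8, over 8 | 2g: 1-10, 11-30, over 30 |
| Physician | 4f: 1-4, 5-8, over 8 | 4g: 1-10, 11-30, over 30 |
| Emergency room | 12e: 1-4, 5-8, over 8 | 12f: 1-4, 5-8, over 8 |
| Urgent care | 13e: 1-4, 5-8, over 8 | 13f: 1-4, 5-8, over 8 |

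The two lower codes of 12f and 13f both fall inside the 1-10 band of 2g and 4g. The top code covers 9-10 minutes (part of the first band), all of 11-30 and all of over 30, so it cannot be assigned to any one of them. Trips of 9 and 90 minutes share it.

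**What the minute bands can separate**

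The documents give no travel speeds. As an assumption, take average speeds of 20 to 60 mph. The longest trip that fits within 8 minutes is speed × 8/60:

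- 20 mph: 20 × 8/60 = 2.7 miles
- 30 mph: 30 × 8/60 = 4.0 miles
- 40 mph: 40 × 8/60 = 5.3 miles
- 60 mph: 60 × 8/60 = 8.0 miles

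The speed needed to stay out of the top band is distance/8 × 60. That is 5/8 × 60 = 37.5 mph for 5 miles and 8/8 × 60 = 60 mph for 8 miles. At 30 mph, a 5-mile trip takes 5/30 × 60 = 10 minutes. So at 30 mph or slower, every trip in the two upper mile bands gets the top minute code, and for those trips the minute item adds nothing to the mile item. This shows the resolution of the item. It does not show how many participants make such trips.

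**Does a common set of bands exist?**

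Bands of 1-4, 5-8, 9-10, 11-30 and over 30 minutes collapse both ways. Merging the last three gives the present 12f/13f scale. Merging the first three gives the 2g/4g scale.

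**The case against.** The strongest reply concerns consequence. A reader might infer that Hypotheses 2.1 and 2.2 and Question 2.1 rest on summed cost and time, and that Aim 2 therefore fails. The documents define no such sum. Hypothesis 2.2 concerns use of services, which the form measures by visit counts, and neither fault touches those. A reader might also infer that the costliest events are distorted. In fact out-of-pocket cost and transport cost for emergency and urgent-care visits are asked in 12c-d and 13c-d of everyone who reports a visit. Nothing in the documents shows that clothing alterations rank among the large costs.

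Other parts of the reply also stand. The 12f and 13f bands are ordered and do not overlap, so a cut at 8 minutes is usable. Distance is asked in the same mile bands for all four visit types, so travel can still be compared by distance. People on the unasked branch of item 30 may include some whose relatives do the work for free. The proposed minute bands are still open above 30. The travel-time items cover only the journey to the visit, so total time to obtain care could not be computed from them even after the edit.

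Two possible defences do not remove the point. Section 12.1 and the SAP mention a variety of sources for Aim 2, but the questionnaire is the only source named for family cost and patient time. The statement in section 12.10 that incurred expenses will not be collected concerns inputs to the intervention, not family spending.

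**Conclusion.** The point holds as a minor form error in three sub-items. For anyone whose alterations are done by another person, alteration spending is unrecorded in every case. For emergency and urgent-care travel, any trip over 8 minutes gets a single code, which cannot be combined with the nurse and physician scale. Both faults recur at baseline and six months.

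The number of participants affected cannot be derived from the documents. That people who pay others spend more, or that most such trips exceed 8 minutes, is plausible but remains an assumption. A reader might infer bias between arms, but both arms complete the same form. The item 30 gap could favour one arm only if the intervention changed who does the alterations, and nothing in the documents shows that. What is shown is lost detail in components of family cost and patient time. The rest of Aim 2 is untouched by these faults. The conclusion rests on the form as printed.

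**What to change.** - **Item 30:** ask the spending question of everyone who says alterations are needed. Keep the self-made question as a separate descriptor, so that cost among self-alterers can still be extracted.
- **Items 12f and 13f:** use 1-4, 5-8, 9-10, 11-30 and more than 30 minutes. New answers can then be set beside 2g and 4g, and answers already collected can still be compared at the 8-minute cut.
- **Data already collected:** report alteration cost as covering self-alterers only. Code the unasked branch as not asked, never as zero. Do not convert 12f or 13f answers to minutes.

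The cost is three small edits to the paper and web forms. The real price is in comparisons over time. Participants whose baseline was on the old form can be compared with their own follow-up only on the coarser minute bands and only on self-made alteration cost. If data collection is complete, the reporting rules in the third bullet are the whole of the fix.
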